#### **7.1.5 Visit Requirements**

Visit requirements are outlined in Section 6.0 - Trial Flow Chart. Specific procedure-related details are provided above in Section 7.1 - Trial Procedures.

##### **7.1.5.1 Screening**

Approximately 30 days prior to treatment allocation/randomization, potential candidates to be enrolled in this trial will be evaluated to determine that they fulfill the entry requirements as set forth in Section 5.1. Screening procedures may be repeated after consultation with the Sponsor.

If additional time is needed for screening procedures, an extension of the screening window by up to 7 days may be approved following mandatory Sponsor consultation.

##### **7.1.5.2 Treatment Period**

The treatment period will continue every 21 days for up to 35 cycles (approximately 2 years) as long as subjects are receiving benefit from trial treatment and have not had disease progression or met any criteria for study withdrawal. Please refer to section 5.8.2.

##### **7.1.5.3 Safety Follow-Up Visit**

The mandatory Safety Follow-up Visit should be conducted approximately 30 days after the last dose of trial treatment or before the initiation of a new anticancer treatment, whichever comes first. This visit may be combined with the EOT visit if a decision is made to end treatment 30 or more days since the last dose of treatment.

All AEs that occur prior to the Safety Follow-Up Visit should be recorded. Subjects with an AE of Grade >1 will be followed until the resolution of the AE to Grade 0-1 or until the beginning of a new anticancer therapy, whichever occurs first. Serious AEs that occur within 90 days of the end of treatment or before initiation of a new anticancer treatment should also be followed and recorded.

#### **7.1.5.4 Discontinued Subjects Continuing to be Monitored in the Trial**

Subjects will be required to return to the clinic approximately 30 days after the last dose of trial treatment for a safety follow-up visit. Subjects should report any AEs up to 90 days after the last dose of the trial treatment. A serious adverse event considered drug-related by the investigator should be reported regardless of how long has elapsed since treatment cessation.

### **7.2 Assessing and Recording Adverse Events**

An adverse event is defined as any untoward medical occurrence in a patient or clinical investigation subject administered a pharmaceutical product and which does not necessarily have to have a causal relationship with this treatment. An adverse event can therefore be any unfavourable and unintended sign (including an abnormal laboratory finding, for example), symptom, or disease temporally associated with the use of a medicinal product or protocol-specified procedure, whether or not considered related to the medicinal product or protocol-specified procedure. Any worsening (i.e., any clinically significant adverse change in frequency and/or intensity) of a preexisting condition that is temporally associated with the use of the Sponsor's product, is also an adverse event.

Changes resulting from normal growth and development that do not vary significantly in frequency or severity from expected levels are not to be considered adverse events. Examples of this may include, but are not limited to, teething, typical crying in infants and children and onset of menses or menopause occurring at a physiologically appropriate time.

Sponsor's product includes any pharmaceutical product, biological product, device, diagnostic agent or protocol-specified procedure, whether investigational (including placebo or active comparator medication) or marketed, manufactured by, licensed by, provided by or distributed by the Sponsor for human use.

Adverse events may occur during clinical trials, or as prescribed in clinical practice, from overdose (whether accidental or intentional), from abuse and from withdrawal.

Progression of the cancer under study is not considered an adverse event.

All adverse events that occur after the consent form is signed but before treatment allocation/randomization must be reported by the investigator if they cause the subject to be excluded from the trial, or are the result of a protocol-specified intervention, including but not limited to washout or discontinuation of usual therapy, diet, placebo treatment or a procedure. From the time of treatment allocation/randomization through 30 days following cessation of treatment, all adverse events must be reported by the investigator. Such events will be recorded at each examination on the Adverse Event case report forms/worksheets. The reporting timeframe for adverse events meeting any serious criteria is described in section 7.2.3.1. The investigator will make every attempt to follow all subjects with non-serious adverse events for outcome.

Electronic reporting procedures can be found in the Electronic Data Capture (EDC) data entry guidelines. Paper reporting procedures can be found in the Investigator Trial File Binder (or equivalent).

### **7.2.1 Definition of an Overdose for This Protocol and Reporting of Overdose to the Sponsor**

For purposes of this trial, an overdose of pembrolizumab will be defined as any dose of 1000 mg or greater ( $\geq 5$  times the indicated dose).

No specific information is available on the treatment of overdose of pembrolizumab. In the event of overdose, the subject should be observed closely for signs of toxicity. Appropriate supportive treatment should be provided if clinically indicated.

If an adverse event(s) is associated with (“results from”) the overdose of Sponsor's product or vaccine, the adverse event(s) is reported as a serious adverse event, even if no other seriousness criteria are met.

If a dose of Sponsor's product or vaccine meeting the protocol definition of overdose is taken without any associated clinical symptoms or abnormal laboratory results, the overdose is reported as a non-serious Event of Clinical Interest (ECI), using the terminology “accidental or intentional overdose without adverse effect.”

All reports of overdose with and without an adverse event must be reported by the investigator within 24 hours to the Sponsor either by electronic media or paper. Electronic reporting procedures can be found in the EDC data entry guidelines. Paper reporting procedures can be found in the Investigator Trial File Binder (or equivalent).

### **7.2.2 Reporting of Pregnancy and Lactation to the Sponsor**

Although pregnancy and lactation are not considered adverse events, it is the responsibility of investigators or their designees to report any pregnancy or lactation in a subject (spontaneously reported to them) that occurs during the trial.

Pregnancies and lactations that occur after the consent form is signed but before treatment allocation/randomization must be reported by the investigator if they cause the subject to be excluded from the trial, or are the result of a protocol-specified intervention, including but not limited to washout or discontinuation of usual therapy, diet, placebo treatment or a procedure. Pregnancies and lactations that occur from the time of treatment allocation/randomization through 120 days following cessation of Sponsor's product, or 30 days following cessation of trial treatment if the subject initiates new anticancer therapy, whichever is earlier, must be reported by the Investigator. All reported pregnancies must be followed to the completion/termination of the pregnancy. Pregnancy outcomes of spontaneous abortion, missed abortion, benign hydatidiform mole, blighted ovum, fetal death, intrauterine death, miscarriage and stillbirth must be reported as serious events (Important Medical Events). If the pregnancy continues to term, the outcome (health of infant) must also be reported.

Such events must be reported within 24 hours to the Sponsor either by electronic media or paper. Electronic reporting procedures can be found in the EDC data entry guidelines. Paper reporting procedures can be found in the Investigator Trial File Binder (or equivalent).

Although pregnancy and lactation are not considered adverse events, it is the responsibility of investigators or their designees to report any pregnancy or lactation in a subject (spontaneously reported to them), including the pregnancy of a male subject's female partner that occurs during the trial.

Pregnancies and lactations of subjects and female partners of male subjects from the time the consent form is signed but before treatment allocation/randomization must be reported by the investigator if they cause the subject to be excluded from the trial, or are the result of a protocol-specified intervention, including but not limited to washout or discontinuation of usual therapy, diet, placebo treatment or a procedure. Pregnancies and lactations in subjects and female partners of male subjects that occur from the time of treatment allocation/randomization through 120 days following cessation of Sponsor's product, or 30 days following cessation of trial treatment if the subject initiates new anticancer therapy, whichever is earlier, must be reported by the Investigator. All reported pregnancies must be followed to the completion/termination of the pregnancy. Pregnancy outcomes of spontaneous abortion, missed abortion, benign hydatidiform mole, blighted ovum, fetal death, intrauterine death, miscarriage and stillbirth must be reported as serious events (Important Medical Events). If the pregnancy continues to term, the outcome (health of infant) must also be reported.

Such events must be reported within 24 hours to the Sponsor either by electronic media or paper. Electronic reporting procedures can be found in the EDC data entry guidelines. Paper reporting procedures can be found in the Investigator Trial File Binder (or equivalent).

### **7.2.3 Immediate Reporting of Adverse Events to the Sponsor**

#### **7.2.3.1 Serious Adverse Events**

A serious adverse event is any adverse event occurring at any dose or during any use of Sponsor's product that:

- Results in death;
- Is life threatening;
- Results in persistent or significant disability/incapacity;
- Results in or prolongs an existing inpatient hospitalization;
- Is a congenital anomaly/birth defect;
- Is another important medical event.

**Note:** In addition to the above criteria, adverse events meeting either of the below criteria, although not serious per ICH definition, are reportable to the Sponsor in the same timeframe as SAEs to meet certain local requirements. Therefore, these events are considered serious by the Sponsor for collection purposes.

- Is a new cancer (that is not a condition of the study);
- Is associated with an overdose.

Refer to [Table 7](#) for additional details regarding each of the above criteria.

Progression of the cancer under study is not considered an adverse event unless it results in hospitalization or death.

For the time period beginning when the consent form is signed until treatment allocation/randomization, any serious adverse event, or follow up to a serious adverse event, including death due to any cause, that occurs to any subject must be reported within 24 hours to the Sponsor if it causes the subject to be excluded from the trial, or is the result of a protocol-specified intervention, including but not limited to washout or discontinuation of usual therapy, diet, placebo treatment or a procedure.

For the time period beginning at treatment allocation/randomization through 90 days following cessation of treatment, any serious adverse event, or follow up to a serious adverse event, including death due to any cause, whether or not related to the Sponsor's product, must be reported within 24 hours to the Sponsor either by electronic media or paper. Electronic reporting procedures can be found in the EDC data entry guidelines. Paper reporting procedures can be found in the Investigator Trial File Binder (or equivalent).

Additionally, any serious adverse event, considered by an investigator who is a qualified physician to be related to the Sponsor's product that is brought to the attention of the investigator at any time outside of the time period specified in the previous paragraph also must be reported immediately to the Sponsor.

All subjects with serious adverse events must be followed up for outcome.

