## 1.0 TRIAL SUMMARY

Abbreviated Title	A Prospective, Open-label, Phase 4 Study to Evaluate the Safety of Pembrolizumab (KEYTRUDA®) in Subjects with Unresectable or Metastatic Melanoma or PD-L1 positive Non-small Cell Lung Cancer (NSCLC) in India (Keynote-593)
Sponsor Product Identifiers	MK-3475 Pembrolizumab (Keytruda®)
Trial Phase	4
Clinical Indication	Unresectable or metastatic melanoma, and non-small cell lung cancer (NSCLC) subjects who are either untreated (PD-L1 $\geq 50\%$ ) or have experienced disease progression after a platinum-containing systemic therapy (PD-L1 $\geq 1\%$ )
Trial Type	Interventional
Type of control	No treatment control
Route of administration	Intravenous
Trial Blinding	Unblinded Open-label
Treatment Groups	Pembrolizumab (Keytruda®)
Number of trial subjects	Approximately 150 subjects will be enrolled, with a minimum of 25 unresectable or metastatic melanoma subjects.
Estimated duration of trial	The Sponsor estimates the trial will end approximately 2 years from the time the last subject provides documented informed consent.
Duration of Participation	
Each subject will participate in the trial from the time the subject provides documented informed consent through the final protocol-specified contact.
 
After a screening phase of 30 days, each subject will be assigned to receive trial treatment with pembrolizumab monotherapy until disease progression is confirmed by the site per Response Evaluation Criteria in Solid Tumors (RECIST 1.1), unacceptable adverse event(s), intercurrent illness that prevents further administration of treatment, Investigator's decision to withdraw the subject, non-compliance with trial treatment or procedures requirements or administrative reasons requiring cessation of treatment, or until the subject has received 35 cycles of pembrolizumab (approximately 2 years), whichever occurs first. Each cycle is defined as 21 days.
 
After the end of treatment, each subject will be followed for the occurrence of adverse events and spontaneously reported pregnancy as described under Section 7.2 of the protocol.
 
Subjects who discontinue for reasons such as radiologic or clinical disease progression, safety events, or investigator or subject decision to stop treatment will have an end of treatment (EOT) visit and a 30-day safety follow-up visit per Section 7.1.4.1.

A list of abbreviations used in this document can be found in Section 12.6.

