## 2.0 TRIAL DESIGN

### 2.1 Trial Design

[figure not shown]
This is a nonrandomized, open-label Phase 4 trial to evaluate the safety of pembrolizumab in India in subjects with unresectable or metastatic melanoma, and non-small cell lung cancer (NSCLC) subjects who are either untreated (programmed cell death ligand 1 [PD-L1]  $\geq 50\%$ ) or have experienced disease progression after a platinum-containing systemic therapy (PD-L1  $\geq 1\%$ ). The trial will be conducted in conformance with Good Clinical Practices (GCP). Approximately 150 subjects are planned to be enrolled in this study in India, with a minimum of 25 unresectable or metastatic melanoma subjects. Subjects who are eligible per this protocol to receive a fixed dose of 200 mg intravenous (IV) pembrolizumab every 3 weeks for up to 35 cycles will be enrolled after obtaining documented informed consent and audiovisual recording of the consenting process, as per local regulatory requirements. Subjects will have a follow-up visit 30 days after the last dose of pembrolizumab or before the start of a new antineoplastic therapy, whichever is earlier. The objective of this study is to assess the safety of pembrolizumab in India in subjects with unresectable or metastatic melanoma, and metastatic and advanced NSCLC subjects who are either untreated (PD-L1  $\geq 50\%$ ) or have experienced disease progression after a platinum-containing systemic therapy (PD-L1  $\geq 1\%$ ). This is not a hypothesis-driven study.

Specific procedures to be performed during the trial, as well as their prescribed times and associated visit windows, are outlined in the Trial Flow Chart - Section 6.0. Details of each procedure are provided in Section 7.0 – Trial Procedures.

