### 5.2.1.2 Dose Modification (Escalation/Titration/Other)

#### 5.2.1.2.1 Immune-Related Events and Dose Modification (Withhold, Treat, Discontinue)

##### **Dose Modification and Toxicity Management for Immune-related AEs Associated with Pembrolizumab**

AEs associated with pembrolizumab exposure may represent an immune-related response. These irAEs may occur shortly after the first dose or several months after the last dose of pembrolizumab treatment and may affect more than one body system simultaneously. Therefore, early recognition and initiation of treatment is critical to reduce complications. Based on existing clinical study data, most irAEs were reversible and could be managed with interruptions of pembrolizumab, administration of corticosteroids and/or other supportive care. For suspected irAEs, ensure adequate evaluation to confirm etiology or exclude other causes. Additional procedures or tests such as bronchoscopy, endoscopy, skin biopsy may be included as part of the evaluation. Based on the severity of irAEs, withhold or permanently discontinue pembrolizumab and administer corticosteroids.

Dose Modification and Toxicity Management Guidelines for irAEs associated with pembrolizumab monotherapy, coformulations, or IO combinations are provided in [Table 4](#).

**Table 4 Dose Modification and Toxicity Management Guidelines for Immune-related Adverse Events Associated with Pembrolizumab Monotherapy, Coformulations or IO Combinations**

General instructions:				
irAEs	Toxicity Grade (CTCAEv4.0)	Action With Pembrolizumab Monotherapy, Coformulations or IO Combinations	Corticosteroid and/or Other Therapies	Monitoring and Follow-up
Pneumonitis	Grade 2	Withhold	

Administer corticosteroids (initial dose of 1-2 mg/kg prednisone or equivalent) followed by taper

	

Monitor participants for signs and symptoms of pneumonitis

Evaluate participants with suspected pneumonitis with radiographic imaging and initiate corticosteroid treatment

Add prophylactic antibiotics for opportunistic infections

	Recurrent Grade 2 or Grade 3 or 4	Permanently discontinue		

irAEs	Toxicity Grade (CTCAEv4.0)	Action With Pembrolizumab Monotherapy, Coformulations or IO Combinations	Corticosteroid and/or Other Therapies	Monitoring and Follow-up

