## **5.8 Subject Withdrawal/Discontinuation Criteria**

### **5.8.1 Discontinuation of Treatment**

Discontinuation of pembrolizumab does not represent withdrawal from the trial.

As certain data on clinical events beyond trial treatment discontinuation may be important to the study, they must be collected through the subject's last scheduled follow-up, even if the subject has discontinued trial treatment. Therefore, all subjects who discontinue trial treatment prior to completion of the treatment period will still continue to participate in the trial as specified in Section 6.0 – Trial Flow Chart and Section 7.1.5.3 – Discontinued Subjects Continuing to be Monitored in the Trial.

Subjects may discontinue trial treatment at any time for any reason or be dropped from trial treatment at the discretion of the investigator should any untoward effect occur. In addition,

a subject may be discontinued from trial treatment by the investigator or the Sponsor if trial treatment is inappropriate, the trial plan is violated, or for administrative and/or other safety reasons. Specific details regarding procedures to be performed at trial treatment discontinuation are provided in Section 7.1.4 – Other Procedures.

A subject must be discontinued from trial treatment but continue to be monitored in the trial for any of the following reasons:

1. The subject or subject's legally acceptable representative requests to discontinue trial treatment.
  - Confirmed radiographic disease progression by RECIST 1.1 outlined in Section 7.1.5
  - Unacceptable adverse experiences as described in Section 7.2
  - Any progression or recurrence of any malignancy, or any occurrence of another malignancy that requires active treatment
  - Intercurrent illness other than another malignancy as noted above that prevents further administration of treatment
  - Recurrent Grade 2 pneumonitis
  - A confirmed positive serum pregnancy test
  - Non-compliance with trial treatment or procedure requirements
  - Investigator's decision to discontinue treatment
  - Completion of 35 cycles with pembrolizumab
  - Note: 35 cycles (approximately. 2 years) are calculated from the first dose (Cycle 1 Day 1)

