## **5.10 Beginning and End of the Trial**

The overall trial begins when the first subject (or their legally acceptable representative) provides documented informed consent. The overall trial ends when the last subject completes the last study-related phone-call or visit, withdraws from the trial or is lost to follow-up (i.e. the subject is unable to be contacted by the investigator).

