
1. Documented informed consent and audiovisual recording of the documented informed consent process must be obtained prior to performing any protocol-specific procedure. Results of a test performed as part of routine clinical management are acceptable in lieu of a screening test if performed within 30 days prior to Cycle 1, Day 1). Assign Baseline number when the study informed consent is documented.
 
2. Includes history of treatment for the primary diagnosis, including prior systemic, radiation treatment and surgical treatment, and best response to prior systemic treatments within the previous 10 years. Date of last prior cancer treatment must be documented. Radiographic studies performed prior to study entry may be collected for review by the investigator. Report complete medication history taken within 30 days prior to the screening visit (Visit 1).
 
3. All AEs should be reported for at least 30 days following treatment cessation. Serious adverse events and ECIs should be reported for 90 days following treatment cessation. A serious adverse event considered drug-related by the investigator should be reported regardless of how long has elapsed since treatment cessation. Pregnancies and lactation events should be reported for 120 days following treatment cessation or for 30 days if the subject initiates new anticancer therapy.
 
4. ECOG of 0 or 1 is required at screening and at C1D1.
 
5. Vital signs to include temperature, pulse, respiratory rate, and blood pressure. If a subject's baseline weight does not fluctuate by more than 10%, this weight can be used to calculate dose. Height will be measured at screening only.
 
6. A 12-lead ECG will be performed at Screening and at every fourth cycle starting on Cycle 4.
 
7. Routine laboratory tests (serum or plasma chemistry and hematology) for screening must be performed within 10 days prior to administration of the first dose. If a subject starts screening > 10 days prior to administration of trial treatment, a second screening visit is required to collect the lab specimens within the specified timeframe.
 
8. Testing will be performed by the local laboratory at Screening: Hepatitis B and C serologies should be obtained for subjects without a known history of hepatitis B or C. Those with a known history are ineligible. Include HCV RNA (qualitative) and HbsAg.
 
9. For females of reproductive potential, urine or serum pregnancy test should be performed within 72 hours prior to day 1 of each treatment cycle and 30 days post treatment if required or as specified per local regulatory guidance. A serum test can be done if urine is not appropriate. Additionally, if urine test is positive or is not evaluable, a serum test is required. Subjects must be excluded/discontinued in the event of a positive test result.
 
10. PT/INR and aPTT should be collected at Screening and at the Safety Follow-up Visit after discontinuation of study therapy. Coagulation parameters will be determined throughout the study if clinically indicated. PT/INR and aPTT will be analyzed by the local study site laboratory.
 
11. Routine laboratory tests (e.g., CBC with differential, comprehensive serum or plasma chemistry panel, and urinalysis) will be performed by the local study site laboratory or their contract laboratory. Additionally, CBC with differential and comprehensive serum or plasma chemistry panel are to be collected up to 48 hours prior to Day 1 dosing of any Cycle.
 
12. Following baseline and Cycle 2, urinalysis should be performed every fourth cycle.
 
13. Analysis of T3, FT4, and TSH will be performed by the local study site laboratory or their contract laboratory. Following Cycle 2, testing will be performed every other cycle.
													

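### SAEs must be reported for 90 days after treatment, but no contact is scheduled after the safety visit at about day 30, so new late SAEs depend on self-report

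*Combined protocol and SAP*

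**What the plan says.** **Reporting period.** Section 7.2.3.1 requires SAE reports "beginning at treatment allocation/randomization through 90 days following cessation of treatment, any serious adverse event", whether or not related and including death from any cause. Flow-chart footnote 3 agrees: "Serious adverse events and ECIs should be reported for 90 days following treatment cessation". Drug-related SAEs have no time limit.

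**Scheduled contact.** Section 2.1 plans a "follow-up visit 30 days after the last dose of pembrolizumab or before the start of a new antineoplastic therapy", whichever comes first. This is the last column of the flow chart (Section 6.0). The chart and Section 7.1.4.1 time the visit from the end-of-treatment (EOT) visit, and the chart allows +7 days. Footnote 17 lets the two visits be combined when the decision to stop comes 30 or more days after the last dose.

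**After that visit.** Section 7.1.5.4 says: "Subjects should report any AEs up to 90 days after the last dose of the trial treatment". Sections 7.1.4.1, 7.1.5.3 and 7.2.3.1 provide follow-up of events already on record. Section 5.8.1 says of clinical events after discontinuation that "they must be collected through the subject's last scheduled follow-up". Section 5.10 says: "The overall trial ends when the last subject completes the last study-related phone-call or visit". No routine call appears in the flow chart.

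**Expected timing of events.** Section 5.2.1.2.1 warns: "These irAEs may occur shortly after the first dose or several months after the last dose of pembrolizumab treatment".

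**The concern.** The plan makes a 90-day SAE window mandatory but schedules contact for only about its first third. A duty to report within 24 hours works only once the site knows of the event. A subject who leaves the day-30 visit with nothing under follow-up, and is admitted with a new SAE on day 60, enters the database only if the site happens to be told. The lost-to-follow-up procedure in Section 7.1.4.1.1 does not help, because it starts from a missed visit and no visit remains to be missed.

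Safety is the sole objective. Table 8 reports the proportions with any SAE and with any serious drug-related AE, over everyone treated (Section 8.5.1). With that denominator fixed, an SAE that is missed in a subject with no other recorded SAE can only lower the proportion, and the confidence interval does not show the loss. Subjects who have progressed and moved to other care are plausibly the hardest to hear from.

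**Working it through.** **The plan's own figures.** Section 8.9.1 tabulates exact (Clopper-Pearson) 95% intervals for N = 150. All seven rows reproduce to one decimal, for example 30/150 = 20.0% (13.9% to 27.3%) and 38/150 = 25.3% (18.6% to 33.1%). The point does not depend on this table; it is used below only for scale.

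**Days without scheduled contact** = day the window closes − day of last scheduled contact.

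Inputs: 90-day window (Section 7.2.3.1, footnote 3); visit at day 30 after last dose (Sections 2.1, 7.1.5.3); +7 days (flow chart).

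- Visit on time: 90 − 30 = 60 days, 60/90 = 67%.
- Visit at +7: 90 − 37 = 53 days, 53/90 = 59%.

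**Effect of the anchor.** Suppose the visit is timed from EOT and the window from the last dose. Assume EOT falls 21 to 28 days after the last dose (this interval is not in the documents).

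- Earliest visit: 21 + 30 = day 51, leaving 90 − 51 = 39 days.
- Latest visit: 28 + 37 = day 65, leaving 90 − 65 = 25 days.
- A combined visit on day d after the last dose leaves 90 − d days, or none if d is 90 or more.
- If window and visit both run from EOT, the gap is 60 days again (53 at +7).

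Section 7.2.3.1 counts from cessation of treatment and does not say which anchor that is.

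**What covers the gap.**

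| Provision | Covers | Finds new-onset SAEs? |
|---|---|---|
| 7.1.4.1 | AEs present at discontinuation | No |
| 7.1.5.3 | AEs above Grade 1, until resolved or new therapy starts | No |
| 7.2.3.1, last line | Outcome of known SAEs | No |
| 7.1.1.4.1 | Review of new antineoplastic therapy | Only incidentally; no contact is scheduled for it |
| 7.1.4.1.1 | Missed visits | No; no visit remains |
| 7.1.5.4 | Any AE to day 90 | Yes, by self-report |

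**Last subject's timeline**, in days from consent, assuming all 30 screening days are used, 35 cycles are given and nothing is delayed:

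- Last dose: 30 + 34 × 21 = 744.
- Safety visit: 744 + 30 = 774.
- SAE window closes: 744 + 90 = 834, about 27 to 28 months.
- Section 1.0 estimates trial end at "approximately 2 years from the time the last subject provides documented informed consent", about 730 days.
- Last scheduled contact to close of window: 834 − 774 = 60 days.

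**Scale only.** The counts here are assumed, because the documents give no late-event rate. Suppose 30/150 subjects have an SAE on record, and 2, 5 or 8 more had a first SAE that was late and unreported. The true figures would then be 32/150 = 21.3% (15.1% to 28.8%), 35/150 = 23.3% (16.8% to 30.9%) or 38/150 = 25.3% (18.6% to 33.1%).

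**The case against.** The best defence is that the plan is not wholly passive. Unresolved AEs above Grade 1 are followed, all SAEs are followed for outcome, and new antineoplastic therapy is reviewed. A Grade 2 event at day 30 that later becomes serious would normally be picked up. This stands, and it confines the point to new-onset events in subjects with nothing under follow-up. The 60-day figure also depends on the last-dose anchor, as shown above.

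Several stronger readings are tempting but are not supported:

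- **That the SAE rates are presented as 90-day rates.** Section 8.6.1 and Table 8 state no post-treatment window for SAEs. The only period named there, the study therapy period, applies to ECIs.
- **That Section 5.8.1 stops collection at day 30.** It sets a minimum and points to the flow chart, whose footnote 3 carries the 90 days.
- **That early new therapy leaves nearly the whole window uncovered.** Section 7.2.3.1 would imply this, but Section 7.1.5.3 can be read as ending SAE collection when new anticancer treatment starts. On that reading no window remains to be missed.
- **That the 120-day pregnancy window has the same defect.** Sections 1.0 and 7.2.2 expressly choose spontaneous reporting, and the window shortens to 30 days with new anticancer therapy.
- **That the rates are biased by a known amount.** No late-event or under-reporting rate is given.
- **That the two-year duration is an error.** It is an approximate estimate, and the longer timeline needs the last subject to complete 35 cycles.

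**Conclusion.** The point holds in this form: SAE reporting is mandatory to day 90, the last scheduled contact is at about day 30 or earlier, and new-onset SAEs after it depend on the subject reporting them. With the visit on time and days counted from the last dose, 60 of 90 days have no scheduled contact (53 at +7). Under mixed anchors or a combined visit the gap is smaller, and it can vanish after a long hold. Across 150 subjects, 150 × 60 = 9,000 person-days is an upper bound, since it assumes that everyone is alive and in follow-up to day 90.

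Late SAEs and deaths may therefore be under-counted in Table 8. If so, the proportions can only be too low, but the amount cannot be derived from the documents. The missing contact is certain from the text; the size of its effect is not. This is a worthwhile, inexpensive improvement, not a flaw that invalidates the trial.

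**What to change.** 1. **Reconcile first.** Decide whether SAE collection ends at new anticancer therapy (Section 7.1.5.3) or continues to day 90 regardless (Section 7.2.3.1). Choose one anchor, last dose or EOT, for both the visit and the window, and define cessation of treatment to match.
2. **Add a flow-chart column:** a telephone contact at day 90 (+7) for every subject alive and not withdrawn, with fixed questions on hospitalisation, new immune-related symptoms and new therapy. Where the subject cannot be reached, ask a family member or the treating physician, so that deaths are found.
3. **Add a day-30 call** for subjects whose safety visit was brought forward by new therapy. The 30-day period for all AEs in Section 7.2 supports it.
4. **Sections 5.8.1 and 5.10:** name the day-90 call as the last scheduled contact.
5. **Section 1.0:** restate the duration to include the 90-day window, up to about 834 days (27 to 28 months) from last consent if the last subject completes 35 cycles.
6. **Section 8.6.1:** state the post-treatment window counted in the SAE proportions.

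Cost: about 150 short calls by existing site staff, a small number of day-30 calls, and up to about two more months (834 − 774 = 60 days) to last contact. No visit or procedure is added.
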